#### Summary tables

- Summary statistics of raw, change, % change and annualized % change by visit and by on/off trt and by brain region

- Repeat after excluding Participants with subdural hematoma

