The **USM Follow-up IN (06-Dec-2022)** was issued by Novartis to inform investigators that Novartis has decided to discontinue development of branaplam as a potential treatment for people with Huntington's disease. The decision followed a review of unblinded data from VIBRANT-HD indicating that the benefit:risk of branaplam in Huntington's disease is not positive. This decision was endorsed by the independent Data Monitoring Committee (DMC) as well as the VIBRANT-HD SC.

Key findings from this review included:

- Increased NfL levels in serum and/or cerebrospinal fluid (CSF) observed in the majority of the participants in active arm.
- Changes in the neurological exam on two consecutive visits, predominantly new hypoactive and/or absent DTRs, observed in more than half of participants in the active arm and the majority of participants with 12 weeks or more of treatment.
- Almost half of the participants in the active arm reported symptoms of peripheral neuropathy, either through the neuropathy questionnaire or as an adverse event report.
- Decreased amplitude (50%) in the sural nerve (SNAP) compared to baseline was observed in 7 participants in active arm.
- Preliminary magnetic resonance imaging (MRI) findings suggestive of an increased volume of the lateral ventricles were seen in majority of patients in active arm.
- Steady state mutant HTT lowering in CSF estimated to be approximately 30% with weekly doses of 56 mg branaplam.

Given the high incidence of signs/symptoms of neurotoxicity at the current dose of branaplam, it is considered highly unlikely that lower doses or different dose regimens can be identified that would be safe and provide clinically meaningful benefit.

With the **USM (06-Dec-2022)** letter, study drug is now permanently discontinued in the VIBRANT-HD study and no further cohorts will be initiated. Both the DMC and the SC recommended that all participants who received active treatment (branaplam) remain in the study for follow-up for approximately one year following initial treatment discontinuation, specifically to continue to assess signs and symptoms of peripheral neuropathy as well as to collect additional MRI data.

Additionally, the allocation to treatment (branaplam or placebo) for each of the participants at the sites was provided to investigators in separate communications.

The following actions were to be taken by sites as part of the update to the USM in the VIBRANT-HD study:

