## Baseline

The baseline value is defined as the last assessment performed prior to start of study treatment. In this study, baseline values will be the values obtained during screening, the week of Baseline or on Day 1. If the Baseline visit is missing or the assessment was not done at Baseline, the last assessment of an earlier visit (scheduled or unscheduled) which is the closest to the Baseline visit will be used as Baseline. In case an assessment is repeated at a later visit during the screening/baseline epoch, the latest one will be used as Baseline. Note: Assessments on the day of randomization are assumed to have been taken as per protocol, i.e. if the assessment should be performed before dosing, the assessment will be treated as pre-dose as per protocol. Practically, i.e. that the time part of the date/time entry will be ignored. Exception: In case there is a protocol deviation or a comment that specifically indicates that the assessment has been taken post-dose, the assessment will not be treated as pre-dose.

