## Post-baseline measurement

Post-baseline measurements are defined as those assessments after the first dose of treatment.

When change from baseline is of interest the following formula will be used for each scheduled visit and time-point where baseline and post-baseline values are both available **except** for volumetric (vol) MRI:

Change from baseline = post-baseline value – baseline value.

Percent (%) change from baseline = (post-baseline value – baseline value)/baseline value\*100%.

Annualized change from baseline = 365.25\*change from baseline/ time interval (in days).

Annualized percent change from baseline = 365.25\*percent change from baseline/time interval (in days).

Time interval = (date of current assessment – date of baseline assessment + 1).

Note for MRI data, change is derived via BSI technique, the changes are already provided in source data (calculation of change and % change for MRI is available in [Section 2.6.2.2](#)).

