### 2.6.2.2 Volumetric MRI

In order to assess atrophy rate, volMRI images from follow-up timepoints are compared to those from earlier timepoints using the boundary shift integral (BSI) technique in selected brain regions. The technique determines the total volume through which the boundaries of a given cerebral structure have moved, and hence, it aims at quantifying the amount of change in these selected brain regions. Absolute volume is provided using Medical Image Display and Analysis Software (MIDAS). BSI change is provided by vendor directly in the database, % change and annualized % change will be derived using BSI change and baseline from MIDAS. The output of the method is a change from BL in volume (atrophy). The direction of change (BSI) varies by region as illustrated in [Table 2-1](#).

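### Annualized MRI change in off-treatment rows is a cumulative average since the pre-dose scan, not an off-drug rate, and no planned summary gives within-person off-drug change

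*SAP*

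**What the plan says.** SAP 2.6.2.2 (Volumetric MRI, Summary tables) lists "Summary statistics of raw, change, % change and annualized % change by visit and by on/off trt and by brain region".

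Four other provisions fix what those statistics mean.

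- **Numerator.** SAP 2.6.2.2 says of the boundary shift integral (BSI) method: "The output of the method is a change from BL in volume (atrophy". It adds that % "change and annualized % change will be derived using BSI change and baseline from MIDAS".
- **Baseline.** SAP 2.1.1 (Baseline): "The baseline value is defined as the last assessment performed prior to start of study treatment".
- **Annualizing interval.** SAP 2.1.1 (Post-baseline measurement) gives "Time interval = (date of current assessment – date of baseline assessment + 1". That block of formulas excludes volumetric MRI and points to 2.6.2.2, which states no interval of its own. The 2.1.1 interval is therefore the default, not an explicit MRI rule.
- **On/off flag.** SAP 2.1.1 (On/off treatment) and 2.6.2.2 set the flag per visit from the collection date. Up to 13 days after the last dose is on treatment; 14 days or more is off.

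The rationale for Protocol Amendment 02 reports preliminary enlargement of the lateral ventricles in the majority of the active arm. It keeps branaplam participants in follow-up for about a year after stopping, to assess neuropathy "as well as to collect additional MRI data". Protocol Table 8-5 schedules brain MRI at Weeks 33, 53 and 69.

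**The concern.** The flag moves a scan into an off-treatment row but does not change the interval over which its change is measured. An off-treatment row therefore carries all the volume change that accrued on branaplam, divided by on-drug plus off-drug time. SAP 2.6.2.2 introduces these measures as a way to assess atrophy rate, so an annualized number in an off-treatment row invites reading as the rate after stopping.

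The natural question for the follow-up scans is whether the enlargement persists, progresses or reverses once drug is stopped. The annualized column can mislead on this in two ways. Under a plateau it declines from visit to visit, which looks like recovery. Under partial reversal it still shows expansion.

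Nothing else planned for MRI fills the gap. The SAP defines recovery for the neurological exam, the neuropathy questionnaire, nerve conduction and NfL (2.7.4.4 to 2.7.4.6 and 2.11.1), but not for MRI, and the combined recovery table in 2.7.4.7 leaves MRI out. Placebo participants may leave at Week 33 (Protocol, text before Table 8-5), so the Week 53 and 69 rows will have little or no placebo comparison.

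**Working it through.** The plan states no figure to reproduce, so the check applies its formulas to an illustration.

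**Inputs from the documents**
- Target days 225, 365 and 477 for Weeks 33, 53 and 69 (Protocol Table 8-5, SAP Table 5-6).
- Baseline scan window Day -14 to -3 (Protocol Table 8-1, footnote).
- Ventricular growth in HD of about 1 %/year (Protocol 8.3.4).

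**Assumptions not in the documents**
- Ventricular volume +10% at the last on-drug scan.
- That scan on Day 113, chosen because 477 - 113 = 364 days matches the roughly one-year follow-up.
- Baseline scan on Day -7.
- Linear change after Day 113.
- The default interval in SAP 2.1.1.

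**Formulas.** Let P be the % change from baseline at the last on-drug scan and C the % change now.
- Tabulated value = 365.25 × C / T, where T is days from baseline scan to current scan, plus 1.
- Off-drug rate = 365.25 × (C - P) / (days since the last on-drug scan), in points of baseline volume.

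The first takes the sign of C and the second the sign of C - P. They are opposite whenever 0 < C < P, whatever positive interval is used.

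**Intervals.** There is no Day 0, so T = 224 + 7 + 1 = 232, 364 + 7 + 1 = 372 and 476 + 7 + 1 = 484 days. Days since Day 113 are 112, 252 and 364.

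| Course after Day 113 | Week | C (%) | Tabulated (%/year) | Off-drug rate (%/year) |
|---|---|---|---|---|
| Plateau | 33 | 10.00 | +15.7 | 0 |
| | 53 | 10.00 | +9.8 | 0 |
| | 69 | 10.00 | +7.5 | 0 |
| Half reversed by Week 69 | 33 | 8.46 | +13.3 | -5.0 |
| | 53 | 6.54 | +6.4 | -5.0 |
| | 69 | 5.00 | +3.8 | -5.0 |
| HD growth, +1 %/year | 33 | 10.31 | +16.2 | +1.0 |
| | 53 | 10.69 | +10.5 | +1.0 |
| | 69 | 11.00 | +8.3 | +1.0 |

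Examples at Week 69:
- Plateau: 365.25 × 10 / 484 = 7.5.
- Half reversal: 365.25 × 5 / 484 = 3.8, against 365.25 × (5 - 10) / 364 = -5.0. Expressed relative to the volume at the Day 113 scan, the latter is -5.0 / 1.10, or about -4.6.

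**Range of P.** For half reversal at Week 69, P = 2% gives +0.75 against -1.0 %/year, P = 5% gives +1.9 against -2.5, and P = 20% gives +7.5 against -10.0.

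**Range of baseline date.** For the plateau at Week 69, Day -14 gives T = 491 and 7.4 %/year; Day -3 gives T = 480 and 7.6 %/year. No sign changes.

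**The case against.** The strongest reply is that the column sits beside others that correct it. The same table gives raw volume, change and % change by visit, and SAP 2.6.2.2 also plans individual plots of change and % change at actual weeks. In the plateau case % change reads 10, 10, 10, which is plainly persistence; a falling series is reversal. This stands. A reader might infer that the planned tables cannot tell persistence, expansion and reversal apart, or that every tabulated MRI value is a change from baseline. Neither is supported: raw volumes are absolute, and the other columns and plots show the course. What remains is that means by visit and on/off status may come from different participants, and no planned summary pairs scans within a person across the stop of treatment.

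It is also fair that the SAP never calls the figure an off-drug rate. It names it as change from baseline, and the misreading comes from where the figure is placed.

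Two textual defences carry less weight. SAP 2.6.2.2 says "volMRI images from follow-up timepoints are compared to those from earlier timepoints", which could suggest scan-to-scan comparison, but the same paragraph states that the output is change from baseline, and the planned mean plot is from baseline. The exclusion of MRI from the 2.1.1 formulas does leave the exact denominator unstated, including the extra day in it, so nothing here should rest on that detail. The sign result does not depend on it.

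Finally, this is a descriptive analysis for an abbreviated report, with no testing. That limits the consequence but does not make the column informative.

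**Conclusion.** The point holds for the annualized column only. In off-treatment rows that column is a cumulative average since the pre-dose scan. It overstates expansion under a plateau or ordinary HD growth, and it has the opposite sign to the off-drug rate whenever volume is falling but still above baseline. The same logic applies to caudate and whole brain with the direction reversed.

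The structure follows from the SAP's own definitions. The sizes do not: they rest on an assumed on-drug change, scan dates and linear course. A reader might infer that ventricular volumes did reverse, or that the true distortion is several percentage points a year. The documents give no size for the enlargement and do not say that it reversed.

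This is a worthwhile, inexpensive improvement to the MRI summaries, not a defect that hides the result.

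**What to change.** In SAP 2.6.2.2:

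1. Keep change and % change from baseline, labelled as cumulative since baseline.
2. Do not present annualized change from baseline as an off-treatment statistic. If it is kept, label it as since baseline, on plus off drug.
3. For participants with an on-treatment follow-up scan and a later off-treatment scan, add the paired change and annualized change from the last on-treatment scan. Use the difference in BSI change, or the vendor's direct BSI between those two scans if available, over the days between them. State whether the percentage is of baseline volume or of volume at the reference scan.
4. Report separately those whose first follow-up scan was already off treatment, so that two kinds of reference are not mixed. The first post-baseline MRI target in SAP Table 5-6 is Day 113, so participants with short exposure may fall here.

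The cost is SAP wording and one derived variable from data already held. Participants without both scans drop out of the paired summary, so its N should be shown. Differencing two BSI values assumes that they are approximately additive, which the documents do not state; a direct BSI between the two scans would avoid that assumption.

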### Figures

- Spaghetti plot of change, and % change over time (at actual weeks) and by treatment group and by brain region
- Mean % change from baseline with error bars (standard error) will be provided by group at scheduled timepoint (group average and N will be added on x-axis)
- Repeat after excluding Participants with subdural hematoma

#### 2.6.2.3 Pharmacokinetic (PK) endpoints

Sample analysis have been executed using all PK samples available and reconciled by SGS. PK samples are only analyzed for participants on active treatment. Therefore, the population of this PK report is the active treatment participants whose PK samples were analyzed.

PK parameters will be estimated using actual times. All unscheduled samples will be reviewed and used for PK parameter analysis if they could be assigned to nominal collection times and are within the treatment period. Unscheduled samples collected outside of the treatment period will not be used for PK parameter assessment if the use cannot be justified.

Only few samples have been collected at 12 h at week 1 and week 17. The concentrations at 12 h will be listed in the concentration listings and presented in the individual spaghetti plots. The consideration of the samples for PK parameter analysis will be tested in the PK parameter analysis and its use for PK parameter assessment will be decided after data review by the PK expert. Due to the limited number of samples for the 12 h time point compared to the other time points, both time points will not be used for descriptive statistics per timepoint, and not presented in the summary plots.

Outlier in terms of unexpected high or low concentrations will be identified and reviewed during PK parameter estimation. In case an outlier will be identified, the concentration will not be included into the descriptive summary statistics of the concentrations at the respective timepoint and will also not be used for PK parameter derivation. The justification of the exclusion will be added to the concentration data file. The identification of outliers and decision about exclusion of extreme concentration values will be handled by the pharmacokineticist of the study.

### Descriptive statistics of branaplam and UFB112 concentrations

#### Summary tables

The following descriptive summary statistics of branaplam and UFB112 concentrations will be calculated in plasma and CSF for all available visits and timepoints: mean, geometric mean, SD, median, min, max, CV% mean, CV% geometric mean. Geometric mean and CV% will not be calculated in case any value is equal to 0.

### Figures

For branaplam and UFB112 in plasma, spaghetti plots showing longitudinal data of all participants across the complete observation period (from first dosing 0 h, showing concentrations from all available time points and visits, up to the last available time point) will

be presented. In addition, for branaplam and UFB112 in plasma, similar spaghetti plots including only the data over the first week will be presented.

## PK parameters in plasma

### Summary tables

Ctrough will be presented for every visit (from week 2 to week 17). Accumulation ratios between Ctrough later than week 2 and Ctrough at week 2 will be calculated.

For branaplam in plasma, PK parameters including Tmax (h), Cmax (ng/mL), AUC0-168h (h\*ng/mL), AUCinf (h\*ng/mL) will be presented for week 1 and week 17. In addition, the accumulation ratio (the week 17/week 1 ratio of the parameter) will be calculated for Cmax and AUC0-168h.

Note that, at the week 17 visit, the PK sample is not collected at 168 h as per design. As illustrated in [Table 2-2](#), the time 0 h (pre-dose) concentration value will be used as the concentration at 168h, which enables the estimation of the AUC0-168h.

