6.7.2.1 Additional considerations for PK sampling

- On days on which PK samples are obtained (refer to [Section 16.3](#), PK Sample Log), the participant should wait until after the pre-dose PK sample is collected to take the assigned study medication. (The pre-dose PK sample represents the C_{trough} concentration and, therefore, the last dose of branaplam should be 168 h (weekly dose regimen) before the pre-dose PK sample.)
- For the PK samples that are to be collected post dose, (refer to [Section 16.3](#), PK Sample Log), the time of administration is defined as time 0 h; any post dose samples are to be taken as noted as per the visit assessment schedule ([Table 8-2](#), [Table 8-3](#) and [Table 8-4](#)) and [Section 16.3](#). Actual time of samples must be recorded in the eCRF.
- Day 1 - Study participants should avoid any food intake within at least 4 h prior to pre-dose triplicate BP, pulse and ECG assessments/PK sampling on the day of first study drug administration. Breakfast/snack can be served after dose administration. Food intake should further be avoided within at least 4 h prior to the triplicate ECG assessments/PK sampling at 12 hours post dose.
- Week 9 (+/- 1 week) - Food intake should be avoided within at least 4 h prior to the pre-dose triplicate BP, pulse and ECG assessments/PK sampling on week 9 (+/- 1 week)

(breakfast/snack should be served after dose administration). Food intake should further be avoided within at least 4 h prior to the triplicate ECG assessments/PK sampling at 12 hours post dose.

- If the participant has skipped the dose the week prior to the scheduled lumbar puncture, guidance will be provided to the Investigator to clarify which biomarker/pk samples may be deferred to ensure alignment with the planned lumbar puncture. See also [Section 8.5.4.1](#).

7 **Informed consent procedures**

Per the USM follow-up notification dated 06-Dec-2022, sites are required to update and submit for approval an addendum to the Informed Consent that takes into account the changes described in this protocol amendment.

The Investigator or his/her representative will explain the nature of the study, including the risks and benefits, to the participant or their legally authorized representative and answer all questions regarding the study.

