8.5 Additional assessments

8.5.2 Pharmacokinetics

As per the USM, PK and blood biomarkers including mHTT/HTT (plasma [REDACTED]) [REDACTED] should only be collected in all randomized participants up to 6 weeks after the last dose of study drug .

Pharmacokinetic (PK) samples will be collected at the visits defined in the assessment schedule. Follow instructions for fasting as outlined in [Section 6.7.2.1](#) and sample collection, numbering, processing, and shipment in the Lab Manual. Refer to [Appendix 16.3](#) for PK sample log. PK samples should be collected as close to the scheduled timepoints as feasible.

An additional blood sample will be collected in the event that a patient experiences an AE which requires premature termination from the study medication.

PK samples from plasma and CSF will be obtained from all participants at all dose levels. Bioanalytical analysis of PK samples will be executed if participant is treated with branaplam and no bioanalysis will be executed in plasma samples if participant is treated with placebo. Branaplam and its metabolite UFB112 will be determined in plasma and CSF by a validated LC-MS/MS method. The anticipated Lower Limit of Quantification (LLOQ) is 0.500 ng/mL. Concentrations will be expressed in mass per volume units and will refer to the free base. Concentrations below the LLOQ will be reported as “zero” and missing data will be labeled as such in the Bioanalytical Data Report.

PK samples remaining after completion of the determination of parent and/or UFB112 may be used for exploratory assessment of metabolites, plasma protein binding or other bioanalytical purposes (e.g. cross check between different sites, stability assessment). Given the exploratory nature of the work, the analytical method used for those assessments will not be validated.

For standard pharmacokinetic abbreviations and definitions see the list provided at the beginning of this protocol. If feasible, the following pharmacokinetic parameters will be determined in plasma after first dosing and at the Week 17 visit using the actual recorded sampling times and non-compartmental method(s) with Phoenix WinNonlin (Version 8 or higher): the maximum concentration (Cmax), the time it takes to reach Cmax (Tmax), AUClast,

AUCtau, AUCinf, T1/2, Vz/F (branaplam only) and CL/F (branaplam only) from the plasma concentration-time data.

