8.5.3 Biomarkers

Per USM, PK and blood biomarkers including mHTT/HTT (plasma [REDACTED]) [REDACTED]
[REDACTED] should only be collected up to 6 weeks after the last dose of study drug.
The 0-Hour timepoint (pre-dose in the protocol pre-USM) is the only required timepoint for collection.

[figure not shown]
Biomarker analyses will be used to investigate the effect of branaplam at the molecular and cellular level as well as to determine how changes in these markers may relate to exposure and clinical outcomes. In addition, potential predictive markers of efficacy, as well as mechanisms of resistance to branaplam treatment will be explored. Additional markers related specifically to Huntington's disease may be assessed. Samples and data may be also used to support development of future companion diagnostic tests.

Sample(s) will be collected at the time point(s) defined in the Assessment Schedule (Table 8-2, Table 8-3 and Table 8-4).

Instructions for sample collection, processing and shipment will be provided in the Laboratory Manual.

Biomarker assessments in blood and CSF

Blood (serum, plasma, PBMC) and CSF will be collected as indicated in Table 8-2, Table 8-3 and Table 8-4 for soluble and/or cell-based markers. These will include [REDACTED]
[REDACTED] NfL [REDACTED]
[REDACTED]

9 Study discontinuation and completion

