## PK parameters in CSF

### Summary tables

Branaplam concentrations (Ctrough) in CSF (ng/ml) and plasma (ng/ml) will be summarized at Week 9 and Week 17, as well as the mean concentration ratios: CSF/plasma and CSF/free plasma. The free plasma concentration will be calculated by multiplying the plasma concentration by the fraction unbound (fu: branaplam 0.349, fu UFB112: 0.0220, DMPK R1900562).

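### The SAP tabulates plasma Ctrough at every visit to Week 17 without requiring a dose about 168 h earlier, so scheduled 0 h samples taken off drug or after a missed dose can enter the trough and accumulation summaries

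*SAP*

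**What the plan says.** **Protocol.** Section 6.7.2.1 says that the pre-dose sample represents Ctrough and that, for this reason, "the last dose of branaplam should be 168 h (weekly dose regimen) before the pre-dose PK sample".

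Section 8.5.2 says that, after the USM, PK samples "should only be collected in all randomized participants up to 6 weeks after the last dose of study drug". Section 8.5.3 adds: "The 0-Hour timepoint (pre-dose in the protocol pre-USM) is the only required timepoint for collection". Section 8 keeps participants on their original visit schedule up to and including Week 29. The Amendment 02 rationale gives Weeks 9, 13, 17 and onward as examples of the visits that continued off drug. Section 12.5.3 sets concentrations below the LLOQ to zero.

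**SAP 2.6.2.3.**
- Concentrations are summarised for all available visits and time points, with the rule: "Geometric mean and CV% will not be calculated in case any value is equal to 0".
- On troughs: "Ctrough will be presented for every visit (from week 2 to week 17". On accumulation: "Accumulation ratios between Ctrough later than week 2 and Ctrough at week 2 will be calculated". Trough spaghetti plots follow, and all of this is repeated for UFB112.
- At Week 17 the 0 h concentration stands in for the uncollected 168 h value in AUC0-168h.
- In the CSF part: "Branaplam concentrations (Ctrough) in CSF (ng/ml) and plasma (ng/ml) will be summarized at Week 9 and Week 17".
- The only exclusion tied to the treatment period reads: "Unscheduled samples collected outside of the treatment period will not be used for PK parameter assessment if the use cannot be justified". A separate review by the pharmacokineticist removes unexpectedly high or low concentrations.

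**The concern.** The 0 h label means different things before and after the stop of dosing. While dosing continued, it marked a trough about one week after a dose. After the stop, it marks any time up to 42 days after the last dose. The SAP has no rule that separates the two when the sample belongs to a scheduled visit. A missed dose while treatment continued raises the same problem.

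PK is a retained secondary objective, and 56 mg weekly is the only dose given. Mean trough and trough accumulation at 56 mg are among the main PK results the study can still deliver. Contamination moves both in one direction, downward.

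**Working it through.** The plan gives no figure to reproduce. I checked which samples can be affected, whether any rule removes them, and how large the effect on a single sample is.

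**1. Which visits.** Plasma PK days (Protocol Table 16-5) are 8, 15, 29, 57, 85 and 113. Doses fall on Days 1, 8, 15 and so on. Intervals from last dose to sample that are longer than 7 days and no longer than 42 days:

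| Visit | Possible days since last dose |
|---|---|
| Week 2 (Day 8) | none |
| Week 3 (Day 15) | 14 |
| Week 5 (Day 29) | 14, 21, 28 |
| Weeks 9, 13, 17 | 14, 21, 28, 35, 42 |

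Week 2 is the denominator of the accumulation ratios and cannot contain washout, so only the numerator is biased.

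**2. Which participants, for Week 17.** Take 05-Aug-2022 as the stop. The Week 17 sample falls 112 days after the first dose.
- It is a proper trough if the dose at +105 days was taken: first dose by 05-Aug minus 105 days = 22-Apr-2022.
- It lies within 42 days of the last dose only if the dose at +70 days was taken: first dose by 05-Aug minus 70 days = 27-May-2022.
- The exposed first-dose dates therefore run from about 23-Apr to 27-May-2022. Using the trial's last dosing date, 08-Aug-2022, moves both ends three days later.

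The same steps put the exposed first doses at 21-May to 24-Jun for Week 13, and at 18-Jun to 22-Jul for Week 9.

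**3. Is anyone exposed?** The documents give no count. The SAP dated 26-Oct-2023 is labelled as before the last visit. The final follow-up visit is Day 477 ± 14 days, so at latest 490 days after first dose. If that visit was within window, at least one branaplam participant was first dosed on or after 26-Oct-2023 minus 490 days = 23-Jun-2022. That participant's Week 9 fell on or after 18-Aug-2022, off drug. The SAP's NfL subgroup with at least 9 weeks of treatment also implies that some participants had less. Both are inferences.

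**4. Size for one sample.** Half-lives of 82.2 to 120 h come from Protocol 4.2. Assuming mono-exponential decline, the ratio to a true trough at *d* days is 2^(−(24*d* − 168)/T½):

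| Days since last dose | T½ 82.2 h | T½ 120 h |
|---|---|---|
| 14 | 0.243 | 0.379 |
| 21 | 0.059 | 0.144 |
| 28 | 0.014 | 0.054 |
| 35 | 0.0035 | 0.021 |
| 42 | 0.0008 | 0.008 |

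**5. When zeros appear.** Predicted steady-state AUCtau at 56 mg is 3098 h·ng/mL. With k = ln2/T½ and e = exp(−168k), model trough = k × 3098 × e/(1 − e) = 8.4 ng/mL (82.2 h) or 10.9 ng/mL (120 h). Concentration falls below the anticipated LLOQ of 0.5 ng/mL about 21 to 29 days after the last dose.

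**6. Illustrative effect on a visit mean.** Arm A was planned at 25 participants, so 25 × 4/5 = 20 active. True trough accumulation is 1/(1 − e) = 1.32 to 1.61. The mean is multiplied by (m × ratio + 20 − m)/20, where m is the number of contaminated samples.
- m = 4 at 35 days: mean falls about 20%; accumulation reads 1.06 to 1.29.
- m = 8 at 35 days: mean falls 39% to 40%; accumulation reads 0.79 to 0.98.
- m = 4 after one missed dose (14 days): mean falls 12% to 15%.

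The values of m are assumptions.

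**The case against.** **Protocol wording.** Section 6.7.2.1 is a scheduling instruction, not a strict definition. The abbreviation list describes Ctrough as the concentration at the last planned time point before dosing, and a sample with no dose to follow arguably fails that. But the SAP invokes neither statement. The abbreviation would not remove a sample taken after a missed dose when the next dose was then given. It also would not touch the by-visit statistics, which take all samples.

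**Outlier review.** The pharmacokineticist may drop unexpectedly low values from both the summaries and the parameter derivation, and a near-zero value in a trough column is a natural candidate. This is a real safeguard, but a discretionary one that depends on the concentration rather than on dosing history. A low value after dosing stops is what one would expect.

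**Stronger readings that a reader might infer.** These are not supported:
- *That the USM contaminates the CSF troughs.* The Amendment 02 rationale ends scheduled lumbar punctures after the USM unless the investigator deems one necessary. Section 6.7.2.1 promises guidance on deferring samples when the dose before a puncture is skipped. The plasma side of that summary remains exposed.
- *That the USM distorts Week 17 AUC0-168h.* With no Week 17 dose there is no post-dose profile. Only a missed dose before an otherwise dosed Week 17 matters.
- *That everyone first dosed after mid-April 2022 has a contaminated Week 17 trough.* Step 2 limits this to about five weeks of first-dose dates.

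**Consequence.** Reporting is descriptive, in an abbreviated report of a terminated programme. Individual plots and listings would show the decline, and mean, SD, median, minimum and maximum survive a zero. This lowers the stakes but does not correct the tabulated trough mean or accumulation ratio.

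**Conclusion.** The concern holds for scheduled plasma 0 h samples. Followed literally, SAP 2.6.2.3 admits samples taken 14 to 42 days after the last dose into the trough table and plot, the accumulation ratios and the by-visit statistics, mainly at Weeks 5 to 17. The direction is certain: trough and accumulation are biased low.

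The effect per sample is large: 24% to 38% of a true trough at 14 days and 1% to 5% at 28 days. It rests on mono-exponential decline, steady state and the healthy-volunteer half-lives. The effect on any visit mean cannot be stated, because the documents do not say how many samples are affected. The 20% and 40% figures are illustrations. The point merits a correction to the SAP; it does not show that any reported result is wrong.

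**What to change.** Define plasma Ctrough in SAP 2.6.2.3 as a 0 h sample taken one dosing interval after an administered dose, using the recorded dosing dates. The tolerance should match the protocol: dosing is allowed ±1 day each week and PK samples move with the visit, so compliant intervals run from 5 to 9 days. A 7 ± 1 day rule would discard compliant samples.

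- Apply the rule to the Ctrough table and plot, the accumulation ratios, the by-visit 0 h statistics, the plasma side of the CSF/plasma summary, and the UFB112 repeats.
- Use the Week 17 0 h value as the 168 h value only when it meets the same rule.
- List all other 0 h samples by days since last dose, and report the number excluded at each visit.

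The cost is one definition and fewer samples at later visits. The wide tolerance also leaves some spread: by the same decay formula, a sample at 5 days is 1.32 to 1.50 times the 7-day value (2^(48/T½)), and one at 9 days is 0.67 to 0.76 times. Actual intervals should therefore be shown in the listing.
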